 Flyers	 Internet/web postings	 Radio
 Posters	 Mass email solicitation	 Telephone
 Letter	 Departmental/Center website	 Television
 Medical record review*	 Departmental/Center research boards	 Newspaper
 Departmental/Center newsletters	 Web-based clinical trial registries	 Clinicaltrials.gov
 YCCI Recruitment database	 Social Media (Twitter/Facebook):	
 Other:		

* Requests for medical records should be made through JDAT as described at
<http://medicine.yale.edu/ycci/oncore/availableservices/datarequests/datarequests.aspx>

3. Recruitment Procedures:

- a. Describe how potential subjects will be identified. Eligibility will be determined by the PI and the study coordinator through chart review. The PI is the director of the Diabetes in Pregnancy clinic and oversees all patients that attend this clinic.
- b. Describe how potential subjects are contacted. Potential subjects will be contacted while they are in the Diabetes in Pregnancy clinic either during their antenatal testing, diabetes nurse educator visit, ultrasound or clinic visit.
- c. Who is recruiting potential subjects? The PI, study coordinator and other members of the study team will recruit subjects.

4. Assessment of Current Health Provider Relationship for HIPAA Consideration:

Does the Investigator or any member of the research team have a direct existing clinical relationship with any potential subject?

Yes, all subjects

Yes, some of the subjects

No

If yes, describe the nature of this relationship.

Members of the research team also provide clinical care for the patients for management of their diabetes, prenatal care and delivery care.

5. Request for waiver of HIPAA authorization: (When requesting a waiver of HIPAA Authorization for either the entire study, or for recruitment purposes only. Note: if you are collecting PHI as part of a phone or email screen, you must request a HIPAA waiver for recruitment purposes.)

Choose one:

For entire study

For recruitment/screening purposes only

For inclusion of non-English speaking subject if short form is being used and there is no translated HIPAA research authorization form available on the University's HIPAA website at hipaa.yale.edu.

- i. Describe why it would be impracticable to obtain the subject's authorization for use/disclosure of this data: Patients will need to be screened prior to enrollment to determine eligibility
- ii. If requesting a waiver of **signed** authorization, describe why it would be impracticable to obtain the subject's signed authorization for use/disclosure of this data: *Write here*

The investigator assures that the protected health information for which a Waiver of Authorization has been requested will not be reused or disclosed to any person or entity other than those listed in this application, except as required by law, for authorized oversight of this research study, or as specifically approved for use in another study by an IRB.

Researchers are reminded that unauthorized disclosures of PHI to individuals outside of the Yale HIPAA-Covered entity must be accounted for in the "accounting for disclosures log", by subject name, purpose, date, recipients, and a description of information provided. Logs are to be forwarded to the Deputy HIPAA Privacy Officer.

6. **Process of Consent/Accent:** Describe the setting and conditions under which consent/assent will be obtained, including parental permission or surrogate permission and the steps taken to ensure subjects' independent decision-making.

Consent will be obtained by a member of the study team during the time of a prenatal visit, ultrasound appointment, antenatal testing appointment or diabetes nurse educator visit. Subjects will be approached and informed of the study. Their care in the Diabetes in Pregnancy Clinic will not be altered if they choose not to participate. Their pregnancy care will continue as scheduled whether they consent to enroll in the study or not.

7. **Evaluation of Subject(s) Capacity to Provide Informed Consent/Accent:** Indicate how the personnel obtaining consent will assess the potential subject's ability and capacity to consent to the research being proposed.

The personnel obtaining study consent will review the patient's chart to ensure the patient has appropriate decision making capacity and ability to consent to the study. The personnel will also employ the teach-back method to ensure the potential study subject understands the study and what it entails.

8. **Non-English Speaking Subjects:** Explain provisions in place to ensure comprehension for research involving non-English speaking subjects. If enrollment of these subjects is anticipated, translated copies of all consent materials must be submitted for approval prior to use.

Spanish speaking subjects are unable to be enrolled at this time as we no longer have a Spanish speaking research coordinator to aid with consent of subjects.

As a limited alternative to the above requirement, will you use the short form* for consenting process if you unexpectedly encounter a non-English speaking individual interested in study participation and the translation of the long form is not possible prior to intended enrollment? YES NO

Note* If more than 2 study participants are enrolled using a short form translated into the same language, then the full consent form should be translated into that language for use the next time a subject speaking that language is to be enrolled.

Several translated short form templates are available on the HRPP website (yale.edu/hrpp) and translated HIPAA Research Authorization Forms are available on the HIPAA website (hipaa.yale.edu). If the translation of the short form is not available on our website, then the translated short form needs to be submitted to the IRB office for approval via modification prior to enrolling the subject. *Please review the guidance and presentation on use of the short form available on the HRPP website.*

If using a short form without a translated HIPAA Research Authorization Form, please request a HIPAA waiver in the section above.

9. **Consent Waiver:** In certain circumstances, the HIC may grant a waiver of signed consent, or a full waiver of consent, depending on the study. If you will request either a waiver of consent, or a waiver of signed consent for this study, complete the appropriate section below.

Not Requesting any consent waivers

Requesting a waiver of signed consent:

Screening only (if for recruitment, the questions in the box below will apply to recruitment activities only)

Entire Study (Note that an information sheet may be required.)

For a waiver of signed consent, address the following:

- Would the signed consent form be the only record linking the subject and the research? **YES** **NO**
- Does a breach of confidentiality constitute the principal risk to subjects? **YES** **NO**

OR

- Does the research pose greater than minimal risk? **YES** **NO**
- Does the research include any activities that would require signed consent in a non-research context? **YES** **NO**

Requesting a waiver of consent:

Screening only (*if for recruitment, the questions in the box below will apply to recruitment activities only*)

Entire Study

For a full waiver of consent, please address all of the following:

- Does the research pose greater than minimal risk to subjects?
 Yes *If you answered yes, stop. A waiver cannot be granted.*
 No
- Will the waiver adversely affect subjects' rights and welfare? **YES** **NO**
- Why would the research be impracticable to conduct without the waiver? Need to perform chart review to determine eligibility prior to consenting patients and the PI has an existing relationship with the patients eligible for participation in the study as she is the head of the Diabetes in Pregnancy Clinic at the Yale Maternal-Fetal Medicine office.
- Where appropriate, how will pertinent information be returned to, or shared with subjects at a later date?
Not applicable, requesting waiver for screening purposes only

SECTION IV: PROTECTION OF RESEARCH SUBJECTS

Confidentiality & Security of Data:

1. What protected health information (medical information along with the HIPAA identifiers) about subjects will be collected and used for the research?
We will look at additional variables within the subjects' protected health information including the patients': age, prior pregnancy and delivery history, BMI, medications during pregnancy, gestational age, antenatal admissions, ultrasound findings, maternal weight at delivery, maternal blood glucose values and neonatal weight at birth, APGAR scores and admission to the NICU.
2. How will the research data be collected, recorded and stored?

Patients' data within the Epic will be reviewed by only the researchers involved in this project. All data extracted from the electronic medical record will be stored with de-identified subject ID number-codes for later analysis. The data will be collected and stored in Yale Box on a Yale University password protected laptop.

3. How will the digital data be stored? CD DVD Flash Drive Portable Hard Drive Secured Server Laptop Computer Desktop Computer Other
4. What methods and procedures will be used to safeguard the confidentiality and security of the identifiable study data and the storage media indicated above during and after the subject's participation in the study? Data extracted from the electronic medical records will be de-identified. Coding for participants will be a password-protected document that will be stored on the Yale Box Drive, a secured server.

All portable devices must contain encryption software, per University Policy 5100. If there is a technical reason a device cannot be encrypted please submit an exception request to the Information Security, Policy and Compliance Office by clicking on url <http://its.yale.edu/egrc> or email [contact]

5. What will be done with the data when the research is completed? Are there plans to destroy the identifiable data? If yes, describe how, by whom and when identifiers will be destroyed. If no, describe how the data and/or identifiers will be secured.

The data will be de-identified and stored on the researchers' laptops and Yale Box Drive. The information will be stored for future research and potentially shared with other researchers, but names and other identifiers will not be shared. Additional permission will not be sought from study participants.

6. If appropriate, has a Certificate of Confidentiality been obtained? *Not applicable*

SECTION V: POTENTIAL BENEFITS

Potential Benefits: Identify any benefits that may be reasonably expected to result from the research, either to the subject(s) or to society at large. (Payment of subjects is not considered a benefit in this context of the risk benefit assessment.)

This study may help to provide evidence that CGM is an acceptable alternative to 4 times daily fingersticks for the management of A2 gestational diabetes, which is the current standard of care. Many women find this level of monitoring difficult to complete and painful, leading to fewer fingersticks and less data for clinicians attempting to manage their medication and their pregnancies to help ensure a good outcome for both mothers and infants and reduce the potential complications of poorly controlled A2 GDM (intrauterine fetal demise, macrosomia, polyhydramnios, postpartum hemorrhage, 3rd and 4th degree lacerations, NICU admissions, neonatal hypoglycemia and respiratory distress). The use of a device that would allow for glucose monitoring without fingersticks is an attractive alternative for both patients and providers and could improve compliance with and management of A2GDM, therefore, improving patient outcomes.

SECTION VI: RESEARCH ALTERNATIVES AND ECONOMIC CONSIDERATIONS

1. **Alternatives:** What other alternatives are available to the study subjects outside of the research? The alternative to the study is to continue routine care with 4 times daily fingersticks for blood glucose monitoring, which half of the study population will continue to do to compare routine practice to CGM for the

management of A2GDM. All patients will continue routine care (including visits, ultrasounds and antenatal testing, as required for A2GDM).

2. **Payments for Participation (Economic Considerations):** Describe any payments that will be made to subjects, the amount and schedule of payments, and the conditions for receiving this compensation.
No compensation will be provided. Study devices will be provided at no cost to the participants.
3. **Costs for Participation (Economic Considerations):** Clearly describe the subject's costs associated with participation in the research, and the interventions or procedures of the study that will be provided at no cost to subjects.
There will be no cost to the subjects. The CGM will be covered by the study investigators and the patient's insurance will cover all routine blood glucose monitoring devices, supplies and medications needed for management of gestational diabetes. There will be no additional clinic visits outside what is already required for routine prenatal care for patients with A2 gestational diabetes.
4. **In Case of Injury:** This section is required for any research involving more than minimal risk, and for minimal risk research that presents the potential for physical harm (e.g., research involving blood draws).
 - a. Will medical treatment be available if research-related injury occurs? Standard measures offered to pregnant patients will be available and patient's will be treated as needed in the clinic or on Labor and Birth at YNHH
 - b. Where and from whom may treatment be obtained? The subject would receive these standard measures through their health care provider team (i.e. physician and nurse)
 - c. Are there any limits to the treatment being provided? No
 - d. Who will pay for this treatment? Insurance will be billed for any potential complications from the device use and the participants will be responsible for any co-pays required by the insurance company for standard treatment.
 - e. How will the medical treatment be accessed by subjects? The subject would be treated immediately with appropriate means available in our hospital and clinic system, as is routine care

IMPORTANT REMINDERS

Will this study have a billable service? Yes No

A billable service is defined as any service rendered to a study subject that, if he/she was not on a study, would normally generate a bill from either Yale-New Haven Hospital or Yale Medical Group to the patient or the patient's insurer. The service may or may not be performed by the research staff on your study, but may be provided by professionals within either Yale-New Haven Hospital or Yale Medical Group (examples include x-rays, MRIs, CT scans, specimens sent to central labs, or specimens sent to pathology). Notes: 1. There is no distinction made whether the service is paid for by the subject or their insurance (Standard of Care) or by the study's funding mechanism (Research Sponsored). 2. This generally includes new services or orders placed in EPIC for research subjects.

If answered, "yes", this study will need to be set up in OnCore, Yale's clinical research management system, for Epic to appropriately route research related charges. Please contact [contact]

Are there any procedures involved in this protocol that will be performed at YNHH or one of its affiliated entities?

Yes No

If Yes, please answer questions a through c and note instructions below.

All involved personnel (physicians, diabetes nurse educators, study coordinators) are familiar with the use of the device and have received training on it previously.

a. Does your YNHH privilege delineation currently include the **specific procedure** that you will perform?

Yes No

b. Will you be using any new equipment or equipment that you have not used in the past for this procedure? Yes

No

c. Will a novel approach using existing equipment be applied? Yes No

If you answered "no" to question 4a, or "yes" to question 4b or c, please contact the YNHH Department of Physician Services ([name]) for prior approval before commencing with your research protocol.

IMPORTANT REMINDER ABOUT RESEARCH AT YNHH

Please note that if this protocol includes Yale-New Haven Hospital patients, including patients at the HRU, the Principal Investigator and any co-investigators who are physicians or mid-level practitioners (includes PAs, APRNs, psychologists and speech pathologists) who may have direct patient contact with patients on YNHH premises must have medical staff appointment and appropriate clinical privileges at YNHH. If you are uncertain whether the study personnel meet the criteria, please telephone the Physician Services Department at [contact]. **By** submitting this protocol as a PI, you attest that you and any co-investigator who may have patient contact has a medical staff appointment and appropriate clinical privileges at YNHH.

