Diabetes complicates 6-7% of pregnancies annually and approximately 85% of these cases are women diagnosed with gestational diabetes (GDM).^{1,2} The prevalence of GDM varies within populations based on obesity rates, maternal age and ethnicity. GDM is diagnosed during the third trimester through a two-step process of a 50-gram oral glucose challenge screen and a subsequent 100-gram oral glucose challenge test if the woman screens positive. Once the diagnosis is confirmed women are asked to monitor their glucose levels with finger sticks at least four times a day [upon waking up (fasting) and after each major meal (breakfast, lunch and dinner)] and medication is added when glucose target goals cannot be reached by diet and exercise alone. Approximately, 15% of women will not reach glucose target goals with diet and exercise alone and will require medication. These women are then diagnosed with class A2 GDM by the White classification of diabetes, which is the standard classification method used to categorize diabetics pregnancy and is standard practice for the Yale Maternal-Fetal Medicine Diabetes Clinic.

Identification of women with GDM who require treatment is essential in optimizing pregnancy outcomes for these women. Treatment of GDM results in lower neonatal morbidity, reduced incidence of large for gestational age infants (LGA), reduced incidence of preeclampsia and shoulder dystocia and a reduced need for cesarean delivery.³⁻⁵ Since LGA infants are at higher risk for hypoglycemia which may necessitate admission to the neonatal intensive care unit (NICU), treatment of GDM reduces the incidence of LGA infants resulting in less hypoglycemia and NICU admissions.

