Screening for gestational diabetes is done by a standard 2-step process. The first test is a 50-gram oral glucose challenge (GCT). If the subject fails this test ($\geq 130\text{mg/dL}$ or $\geq 140\text{mg/dL}$ depending on the laboratory used) then they will require a 100-gram fasting glucose tolerance test (GTT). Alternatively, if the patient has a value of $\geq 200\text{mg/dL}$ on the 50-gram glucose challenge she would be diagnosed with gestational diabetes at that time. For the 100-gram GTT the standard at for Yale Maternal-Fetal Medicine is to use the Carpenter-Coustan criteria to make the diagnosis of gestational diabetes, with the following blood sugar cutoffs at the stated time points: fasting – 95mg/dL , 1 hour – 180mg/dL , 2 hours – 155mg/dL , 3 hours – 140mg/dL . If the patient has 2 or more values above the cutoffs she would be diagnosed with gestational diabetes. Subjects who test positive for gestational

diabetes by either the 50-gram GCT of ≥ 200 mg/dL or by having 2 or more elevated values on the 100-gram GTT are notified by their primary Ob-Gyn provider and referred to the Yale Diabetes in Pregnancy Program for education on their diagnosis, blood sugar monitoring, diet, and exercise. This is standard practice for all pregnant patients receiving this diagnosis and would not be considered an extra visit for study purposes.

They will be introduced to the study at their first visit with the diabetes nurse educator after failing their 3-hour GTT. Patients will then be followed, as is routine practice in the clinic, for a minimum of 1 week to see if their blood sugar values for fasting (< 95 mg/dL) and 1-hour after meals (< 140 mg/dL) are mostly ($> 75\%$) at goal for all time-points tested. Women will use the MyChart Diabetes in Pregnancy log that is standard practice for patients in the Yale Diabetes in Pregnancy clinic. Those women who do not have reliable access to this technology will be allowed to use paper logs. Both types of logs, electronic and paper, are reviewed routinely by the diabetes nurse educator and/or physician in the Yale Maternal-Fetal Medicine clinic.

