Women who do not have at least 75% of their blood sugar values at or below the previously stated goals require medication for management of their gestational diabetes and will be diagnosed as A2GDM. When these women return to the Yale Diabetes in Pregnancy Clinic at Yale Maternal-Fetal Medicine for initiation of medication therapy for gestational diabetes they will again be approached about participating in the study and given time to consider their participation at that visit. Should they require more time and wish to discuss with others outside the clinic visit we will contact the patient again in 1 week to inquire about participation in the study. Women who consent to participation will be randomized to the control group (checking blood glucose as previously done with fasting and 1-hour post meal finger sticks) or to receive the Dexcom G6 CGM device, which is a device to monitor blood glucose continuously for 10 days placed on the upper arm or abdomen. The device will stay in place for the duration of the pregnancy and the sensors will be changes every 10 days, as is standard for this device. This device has been used off-label in pregnant women in previous studies. It complies with the standard of care for monitoring blood sugar values for women with gestational diabetes requiring medication but is a novel approach that does not require multiple finger sticks to monitor blood glucose values. It is FDA approved for use in non-pregnant patients. The device is compatible for use with smartphones. Women who do not have smartphones will receive a receiver if needed.

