Inclusion Criteria: women between 18-50 years old, pregnant, diagnosed with gestational diabetes requiring medication (A2) during pregnancy

Exclusion Criteria: pregestational diabetes, diagnosis with gestational diabetes > 33 weeks gestation (too late in pregnancy for study enrollment due to proximity to delivery), anomalous fetus, fetal growth restriction during current pregnancy diagnosed prior to enrollment, abnormal diagnostic genetic testing or screening for the fetus, twin or higher order multiple gestation, non-compliance with prenatal visits (missing ≥3 visits prior to enrollment), maternal medical comorbidities (lupus, chronic hypertension, cancer, ischemic cardiovascular disease).

9. How will **eligibility** be determined, and by whom?

Eligibility will be determined by the PI and the study coordinator through chart review. The PI is the director of the Diabetes in Pregnancy clinic and oversees all patients that attend this clinic.

10. **Risks:** Describe the reasonably foreseeable risks, including risks to subject privacy, discomforts, or inconveniences associated with subjects participating in the research.

Risks to participating in the research include any risk associated with wearing the continuous glucose monitor. The sensor wires for the CGM go under the skin and the device is placed by the patient after instruction from one of our diabetes nurse educators. The device has been deemed safe for use by the FDA.

The standard of care is fingersticks and the CGM device is deemed to be as safe as fingersticks, which the patients will have been doing up until the point of enrollment.

Patients will be de-identified for data analysis.

There is no anticipated increased risk to the woman or her fetus for women in the CGM group compared to the standard monitoring group (with the glucometer and four times a day fingersticks) based on the use of the CGM alone. The risks to the pregnancy are related to the risks of developing gestational diabetes and are the same for women in the CGM arm and the control arm.

11. **Minimizing Risks:** Describe the manner in which the above-mentioned risks will be minimized.

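### Do the two wordings of the 75%-at-goal rule for A2 GDM leave the trial population undefined?

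*Combined protocol and SAP*

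**What the plan says.** Section I, item 4 (Research Plan) gives the rule in two consecutive paragraphs.

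- **Follow-up sentence.** Women are followed "for a minimum of 1 week to see if their blood sugar values for fasting" and 1-hour post-meal readings "are mostly ($> 75\%$) at goal for all time-points tested". The goals there are strict: under 95 mg/dL fasting and under 140 mg/dL one hour after meals.
- **Diagnosis sentence.** "Women who do not have at least 75% of their blood sugar values at or below the previously stated goals require medication". Its consequence is explicit: these women "require medication for management of their gestational diabetes and will be diagnosed as A2GDM".

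Section I, item 8 (Inclusion/Exclusion Criteria) admits women "diagnosed with gestational diabetes requiring medication (A2) during pregnancy" and repeats no threshold. Item 9 has the principal investigator, who directs the clinic, and the study coordinator determine eligibility by chart review. Section I, item 3 (Background) sets at least four checks a day, "upon waking up (fasting) and after each major meal (breakfast, lunch and dinner").

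**The concern.** The inclusion criterion rests on the A2 diagnosis, and these two sentences give its only numerical form. They differ in three respects:

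1. More than 75% against at least 75%.
2. Below the goal against at or below it.
3. The follow-up sentence adds "at goal for all time-points tested", which can be read as a test at each time of day. The diagnosis sentence reads more naturally as a share of all readings.

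Two people applying different sentences to the same log could disagree on whether a woman is A2, and so on whether she is eligible. One plausible pattern lands on the boundary: every fasting value high and every post-meal value at goal gives 21/28 = 75.0%. If the disagreement were common, the enrolled population could not be reproduced from the text.

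**Working it through.** **Inputs.** Four checks a day (Section I, item 3) over the minimum one week (item 4) give 4 × 7 = 28 readings. Let h be the number of high readings. Ties are left out until step 4.

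**1. Both sentences pooled.**
- Follow-up sentence: (28 − h)/28 > 0.75, so h ≤ 6.
- Diagnosis sentence: (28 − h)/28 ≥ 0.75, so h ≤ 7.
- They disagree only at h = 7, where 21/28 = 75.0%.
- Close by they agree: 20/28 = 71.4% and 20/27 = 74.1% are A2 under both; 21/27 = 77.8% is at goal under both.

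**2. Both sentences per time-point.**
- Each time of day has 7 readings. The shares next to the threshold are 5/7 = 71.4% and 6/7 = 85.7%, so exactly 75% cannot occur.
- With two groups (7 fasting, 21 post-meal), the post-meal shares next to it are 15/21 = 71.4% and 16/21 = 76.2%. Again 75% cannot occur.
- In this week the strict and non-strict percentages classify every log alike.

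**3. One sentence per time-point, the other pooled.**
- Follow-up per time-point, diagnosis pooled: the first allows at most one high value at each of four time-points, so at most 4 in all; the second allows 7. They disagree for every log with 5, 6 or 7 high values, and for logs with 2 to 4 when two or more fall at one time-point.
- The reverse pairing also disagrees. Four high fasting values give 24/28 = 85.7% pooled (at goal), but 3/7 = 42.9% fasting (A2).

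**4. Readings equal to a goal, both pooled.**
- Pivotal: 20 below, 2 equal, 6 above gives 20/28 = 71.4% under the follow-up sentence and 22/28 = 78.6% under the diagnosis sentence.
- Not pivotal: 26 below, 2 equal gives 26/28 = 92.9% and 28/28 = 100%, at goal under both.
- Of the 28 × 29/2 = 406 splits into below, equal and above with at least one equal reading, 175 give opposite answers. These are arithmetic splits. They do not estimate how many women are affected.

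**5. Sample size.** Section I, item 13 assumes 60% incidence under standard monitoring and a 40% effect. Read as a relative reduction, that gives 0.60 × (1 − 0.40) = 0.36. With two-sided alpha 0.05, 80% power and no continuity correction:

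n = [1.96 × √(2 × 0.48 × 0.52) + 0.8416 × √(0.60 × 0.40 + 0.36 × 0.64)]² / 0.24² = (1.3848 + 0.5772)² / 0.0576 = 66.8

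That rounds up to 67 per arm, 134 in all, as planned. The 75% rule does not enter the calculation.

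**6. Where the rule acts.** It is applied before consent and randomisation and is not used afterwards. Whichever wording is followed, both arms are drawn from the same pool. Item 4 also has medication adjusted at the same interval and by the same protocol in both arms.

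**The case for a change.** The strongest case is that an eligibility rule should give one answer for one log, and that the disagreement may not be rare. The documents give no frequency. As an illustration, assume independent readings, none equal to a goal, and a true at-goal share of 0.70, 0.75, 0.80 or 0.85. The chance of exactly 21/28 is then 14.5%, 17.2%, 14.0% or 6.7%. If the follow-up sentence is read per time-point and the diagnosis sentence as pooled, the chance of opposite answers is 35%, 56%, 71% or 69%. One week is also only a minimum: with 8 days, 6/8 = 75% becomes possible per time-point. Several people review logs, and no sentence says which wording takes precedence.

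The textual point stands: the sentences differ, and nothing reconciles them. The rest carries less weight. The percentages rest on assumed shares and on independence, which readings from one woman are unlikely to satisfy; the larger ones also need the two adjacent sentences to be read in different units. Only the diagnosis sentence attaches a consequence, so it is naturally the operative one, and the other describes what routine follow-up looks for. Women are approached when they return to start medication, and eligibility is confirmed from the chart. The documents do not ask eligibility staff to recompute percentages. A shift in case mix could move the true event rate away from 60%, but it would do so in both arms, and the documents give no figure for it.

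**Conclusion.** No change to the design or analysis follows. The two sentences contradict each other at the margin, and the sponsor has to reconcile them as a matter of wording; which version is clinically right is not a statistical question. With both pooled, a complete week and no ties, the disagreement is a single count, 21 of 28. It grows with pivotal ties, and most if the sentences are read in different units.

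The trial's conclusions do not depend on the choice. The rule acts before randomisation, so it cannot bias the comparison between arms, and the 67 per arm is reproduced without it. The enrolled women are those whom one clinic diagnosed as needing medication. Section IV, item 1 lists medications during pregnancy and maternal blood glucose values among the data collected, so their glycaemic status can be described from data rather than inferred from the threshold.

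This rests on two readings of the text: that enrolment follows the clinic's diagnosis, and that the diagnosis sentence is the operative one. If the second is wrong, the case mix shifts at the margin in both arms alike, and the comparison remains sound.
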